10.2 Analysis sets

Safety analysis set (SAF)

All patients who received at least 1 dose of study drug and have post-treatment safety data available will be included in the safety evaluation.

MTD analysis set

All patients who completed Cycle 1 and who took at least 80% of the required total dose (protocol-defined dose reductions will not be considered incompliant) of either study drug (rogaratinib or atezolizumab) during Cycle 1 or discontinued during Cycle 1 due to a DLT will be included in the MTD evaluation.

Efficacy analysis set

All patients who have received at least 1 dose of study drug and who have post-baseline efficacy data available will be included in the efficacy evaluation.

Pharmacokinetics (PK) analysis set (PKS)

All patients who have received at least 1 dose of study drug and with at least 1 valid concentration after first dosing and no important protocol deviations affecting the validity will be included in the PK evaluation.

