6.4.2 Replacement

Replacement of patients may occur in Part A in order to ensure the necessary number of evaluable patients for dose selection (at least 4 patients per tested dose level, a total of 20 evaluable patients). Patients who are not valid for efficacy assessment may be replaced, to ensure at least 26 valid patients for assessment of the RP2D. Patients may be replaced in the following circumstances:

Dose selection:

• Patients who discontinue or took less than 80% of the per protocol required total dose of either study drug (rogaratinib or atezolizumab) during the first cycle due to any reason

23 MAY 2023 Version 6.0 Page: 52 of 181

other than a DLT (note: protocol-defined dose reductions will not be considered incompliant).

Efficacy:

• Patients who took less than 80% of the per protocol required total dose of either study drug (rogaratinib or atezolizumab) during the first two cycles or patients without an efficacy assessment.

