7.4.3 Dose modifications

7.4.3.1 Dose limiting toxicities (DLTs)

A DLT is defined as any of the following TEAEs occurring during Cycle 1 and regarded by the investigators and/or sponsor to be related to rogaratinib or atezolizumab. The CTCAE v 4.03 will be used to assess toxicities / adverse events.

Hematological

- Absolute neutrophil count (ANC) < 500/mm³ for more than 7 days
- Febrile neutropenia (a disorder characterized by an ANC $< 1,000/\text{mm}^3$ and single temperature ≥ 38.3 °C or sustained temperature of ≥ 38.0 °C for more than 1 hour)
- Platelets $< 25,000/\text{mm}^3$
- Hemoglobin < 8.0 g/dL
- Grade 3 hemorrhage associated with thrombocytopenia of \geq Grade 3

Non-hematological

- Any non-hematologic Grade 3 or higher toxicity except:
 - o Grade 3 nausea, vomiting, and fatigue that resolve within 72 hours with or without supportive care.
 - o Grade 3 diarrhea will be classified as DLTs if not resolved to Grade ≤ 2 or baseline following dose interruption of rogaratinib and/or withholding atezolizumab within 3 days with or without supportive care.
 - Laboratory abnormalities of any grade will not be considered toxicity unless deemed clinically significant by the investigator.
 - o Grade 3 hypothyroidism
- Any grade myasthenic syndrome/myasthenia gravis, Guillain-Barré or meningoencephalitis.
- Decrease of three lines or more in visual acuity scales, Grade 2 or higher ocular pain or discomfort, or symptomatic retinal disorders including retinal detachment, RPED, central serous retinopathy or retinal vein occlusions.
- Grade 2 with AST or ALT >3 x ULN and up to 5 x ULN or total bilirubin greater than 1.5 and up to 3 x ULN in absence of an alternative explanations for these elevations.
- Any toxicity not resolving within 21 days at ≤Grade 1 with or without supportive care.

23 MAY 2023 Version 6.0 Page: 57 of 181

Miscellaneous

- In case an unexpected drug-related toxicity is seen more frequently, this toxicity may be declared a DLT for the remainder of the study after thorough consultation between the investigator and the sponsor.
- Any rogaratinib-related toxicity that, at the discretion of the investigator, or his designated associate(s), is thought to warrant withholding the drug for more than 3 consecutive days.
- Such toxicities might be Grade 1 or Grade 2 toxicities which interfere with the activities of daily life (e.g. long-lasting fatigue, or anorexia), making a dose reduction necessary in order to ensure the patient's compliance.

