7.4.3.2.1 Hyperphosphatemia

Dose modifications of rogaratinib for elevated serum phosphate levels ($\geq 7 \text{ mg/dL}$) and management guidance for hyperphosphatemia are presented in Table 7–4.

Table 7–4 Dose modifications of rogaratinib and management for hyperphosphatemia

Serum phosphate	Countermeasures
Initial phosphate value is	Continue rogaratinib at the same dose.
abnormally high, but less than 7 mg/dL	Consider low phosphate diet ^a and / or initiate phosphate chelators.
≥ 7 mg/dL for two weeks despite phosphate lowering treatment	Hold rogaratinib and increase dose of phosphate chelators until recovery below 7 mg/dL.
	Re-start rogaratinib at the same dose level and continue phosphate chelators.
≥ 7 mg/dL despite optimal phosphate lowering treatments and two rogaratinib	Hold rogaratinib and continue phosphate chelators until recovery below 7 mg/dL.
treatment interruptions on the same dose within four weeks	Re-start rogaratinib, but at one dose level lower and continue phosphate chelators.
≥ 7 mg/dL despite optimal phosphate lowering treatments and two rogaratinib	Hold rogaratinib and continue phosphate chelators until recovery below 7 mg/dL.
treatment interruptions within four weeks at 400 mg b.i.d.	Re-start rogaratinib at 400 mg b.i.d. and continue phosphate chelators.

b.i.d. = Twice daily, bis in die.

In case phosphate chelators are not tolerated, low-phosphorus diet should be considered.

For patients with elevated serum phosphate levels ≥ 7 mg/dL, serum phosphate level and standard single 12-lead ECG has to be checked weekly for ≥ 4 weeks until resolution (serum phosphate < 7 mg/dL).

In patients with hypocalcemia of CTCAE Grade ≥ 2 , an additional 12-lead ECG has to be obtained on the day of detection of hypocalcemia and should be repeated as clinically indicated.

b: In case of Grade 2 diarrhea with no signs or symptoms of colitis and that does not resolve within 72 hours with or without supportive care, rogaratinib dosing has to be interrupted until resolution to Grade ≤ 1. No dose reduction is required.

c: If not recovered within 21 days, the study treatment will be permanently discontinued.

d: If dose reductions by more than 2 levels are required, the study treatment will be permanently discontinued.

a: Low phosphate diet can be considered if the patient's nutritional status is not affected.

23 MAY 2023 Version 6.0 Page: 60 of 181

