7.4.3.2.2 Liver toxicity

Dose modifications of rogaratinib for liver toxicity are presented in Table 7–5 and have been adapted based on criteria established for liver toxicity due to atezolizumab concomitant administration. Immune-related hepatitis has been associated with the administration of atezolizumab. Refer to the latest available versions of rogaratinib and atezolizumab IBs for further details. Eligible patients must have adequate liver function, as manifested by measurement of hepatic transaminases and total bilirubin, and liver function will be monitored throughout study treatment. Liver toxicity refers to ALT and/or AST and/or bilirubin increases and graded according to CTCAE v.4.03.

23 MAY 2023 Version 6.0 Page: 61 of 181

Table 7–5: Dose modifications of rogaratinib and atezolizumab for liver toxicity

Toxicity	Modification schedule	
Hepatic event, Grade 1	No modifications. Treat as scheduled and check AST, ALT and bilirubin weekly for at least 4 weeks ^a or until values resolve to within normal limits	
Hepatic event, Grade 2	All events:	
with AST or ALT > 3 x ULN and up to 5 x ULN or total bilirubin greater than 1.5 and	No modification. Check AST, ALT and bilirubin level more frequently until return to baseline value	
up to 3 x ULN in absence of an alternative explanation for these elevations	Events of > 5 days' duration:	
ospianation for those dievations	1. STOP rogaratinib	
	2. STOP atezolizumab	
	 Initiate treatment with 1-2 mg/kg/day oral prednisone or equivalent 	
	 Check AST, ALT and bilirubin level weekly or more frequently till recovery to Grade 0-1 a 	
	 After recovery to Grade 0-1 re-start with rogaratinib -1 DL ^b and atezolizumab 	
	 Permanently discontinue atezolizumab and rogaratinib, and contact sponsor if event does not resolve to Grade 0-1 within 12 weeks 	
Hepatic event, Grade 3	Withdraw patient from study treatment permanently a, c, d and	
with AST or ALT > 3 x ULN with concomitant	contact sponsor	
bilirubin > 2 x ULN in absence of an alternative explanation for these elevations	Consider patient referral to gastrointestinal specialist for evaluation and liver biopsy to establish etiology of hepatic injury	
or with AST or AST > 5 x ULN and/or total bilirubin > 3 x ULN in absence of an	Initiate treatment with 1-2 mg/kg/day oral prednisone or equivalent	
alternative explanation for these elevations	If event does not improve within 48 hours after initiating corticosteroids, considering adding an immunosuppressive agent.	

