4.2 Handling of Dropouts

Pre-screening failure = Subject signed ICF for FGFR testing but, for any reason, did not sign the ICF for study treatment eligibility.

Screening failure = Subject signed ICF for study treatment eligibility but, for any reason (e.g. failure to satisfy the selection criteria), terminated the study before start of study treatment.

Dropout = Subject discontinued study participation prematurely for any reason after start of study treatment. The start of the treatment period is defined by the first administration of study treatment.

Replacement of subjects may occur in Part A in order to ensure the necessary number of evaluable subjects for dose selection (at least 4 subjects per tested dose level, a total of 20 evaluable subjects) and to ensure at least 26 valid subjects for assessment of the RP2D. Subjects maybe replaced in the following circumstances:

Dose selection:

- Subjects who discontinue or took less than 80% of the per protocol required total dose of either study drug (rogaratinib or atezolizumab) during the first cycle due to any reason other than a DLT (*note*: protocol-defined dose reductions will not be considered incompliant).

Efficacy:

- Subjects who took less than 80% of the per protocol required total dose of either study drug (rogaratinib or atezolizumab) during the first two cycles or subjects without an efficacy assessment.

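### The MTD analysis set does not mirror the replacement rule and its 80% dose test is ambiguous; if each drug must reach 80%, some held Cycle 1 DLT patients are neither replaceable nor counted

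*Protocol*

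**What the plan says.** Protocol 10.2 gives two routes into the MTD analysis set. One is completing Cycle 1 with at least 80% of the required dose; the other is stopping in Cycle 1 because of a DLT. The sentence ends "of either study drug (rogaratinib or atezolizumab) during Cycle 1 or discontinued during Cycle 1 due to a DLT will be included". Reductions made under the protocol are excused; interruptions are not mentioned. SAP 5.1 repeats the definition and limits the set to the dose selection part.

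Protocol 6.4.2 allows replacement of patients who discontinued or "took less than 80% of the per protocol required total dose of either study drug (rogaratinib or atezolizumab) during the first cycle", unless the reason was a DLT. SAP 4.2 has the same rule: "either study drug (rogaratinib or atezolizumab) during the first cycle due to any reason other than a DLT".

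Protocol 7.4.3.1 lists DLTs that need not end treatment within Cycle 1:
- a rogaratinib-related toxicity that "is thought to warrant withholding the drug for more than 3 consecutive days";
- a hepatic event, "Grade 2 with AST or ALT >3 x ULN and up to 5 x ULN or total bilirubin" within a stated range. If it lasts more than 5 days, Table 7-5 stops both drugs, and then: "After recovery to Grade 0-1 re-start with rogaratinib -1 DL";
- "Any toxicity not resolving within 21 days at ≤Grade 1 with or without supportive care". The matching instruction is Table 7-3, footnote c: "If not recovered within 21 days, the study treatment will be permanently discontinued".

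Protocol 7.4.3.2 allows rogaratinib to be delayed for up to 21 days after a Cycle 1 DLT, and says that interruptions do not lengthen the cycle.

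**The concern.** A set for estimating a DLT rate should keep everyone who had a DLT, and should apply an exposure test only to those who did not. The replacement rule works that way. The set definition does not: a DLT patient enters only by meeting the dose test or by discontinuing inside Cycle 1. A patient held for a DLT, and resumed or stopped later, may do neither.

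DLT incidence is a primary variable (protocol 5.3), and protocol 10.3.4.1 bases the MTD on the observed DLT rate in the first 21 days. Two rules that disagree about who counts can give two different rates.

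**Working it through.** **Inputs.** Rogaratinib is given twice daily for 21 days (protocol 7.4.1.1), so Cycle 1 has 2 × 21 = 42 doses. Atezolizumab is one infusion on Day 1 (7.4.1.2). Dose selection ends at 20 evaluable patients. Completing Cycle 1 is taken to mean reaching Day 21.

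**Dose count.** 0.80 × 42 = 33.6, so 34 doses are needed. Counted at one dose level:
- 7 missed: 35/42 = 83.3%
- 8 missed: 34/42 = 81.0%
- 9 missed: 33/42 = 78.6%
- 14 missed: 28/42 = 66.7%

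A hold lasting to Day 21 gives 66.7% if it starts on Day 15, 76.2% from Day 17 and 81.0% from Day 18. For example, suppose the hepatic DLT is found at the Day 8 laboratory visit, is still present on Day 15, and is held through Day 21. That patient took 28/42 = 66.7%.

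**The 21-day criterion.** With onset on Day 1, failure to resolve within 21 days is established on Day 22 at the earliest. A patient who is waited on until then has not discontinued during Cycle 1.

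**The rules side by side.** Being replaceable is failing 80% on one drug or the other, for a non-DLT reason. The opposite of failing on one or the other is passing on both. The set says *either*, which allows two readings. Low dosing below means missed doses, not reductions.

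| Cycle 1 course (full Day 1 infusion) | Replaceable | In set if each drug needs 80% | In set if one drug suffices |
|---|---|---|---|
| DLT, discontinued in Cycle 1 | No | Yes | Yes |
| DLT, held, 34 or more of 42 doses | No | Yes | Yes |
| DLT, held, 33 or fewer doses, not discontinued by Day 21 | No | **No** | Yes |
| No DLT, completed, 33 or fewer doses | Yes | No | **Yes** |

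Consistent rules would give opposite answers in the replaceable column and the set column. Each reading breaks in one row, shown in bold.

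**Effect if each drug needs 80%.** Losing one DLT patient changes k/n to (k−1)/(n−1), which is smaller whenever k < n.
- 6/20 = 30.0%; 5/19 = 26.3%; 4/18 = 22.2%
- 8/20 = 40.0%; 7/19 = 36.8%; 6/18 = 33.3%

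With true rate p and lost share f, both assumed, the expected rate on the set is p(1−f)/(1−pf):

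| p | f = 10% | f = 25% | f = 50% |
|---|---|---|---|
| 20% | 18.4% | 15.8% | 11.1% |
| 30% | 27.8% | 24.3% | 17.6% |
| 40% | 37.5% | 33.3% | 25.0% |

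**Effect if one drug suffices.** Each under-dosed patient without a DLT adds to the denominator only. With two such patients beside the 20, 6/20 = 30.0% becomes 6/22 = 27.3% (an illustration).

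**Decision table.** A Beta(1,1) prior, unit probability mass on 0–0.25, 0.25–0.35 and 0.35–1, and DU when P(p > 0.30) > 0.95 reproduce all 116 legible cells in rows 0 to 6 of protocol Table 10-1. By the same calculation, removing one DLT patient turns D or DU into S in nine cells: 3/5, 4/7, 4/8, 5/10, 6/12, 7/14, 8/16, 8/17 and 9/19. At n = 20 one loss changes nothing: 10/20 is DU (P = 0.974) and 9/19 is DU (0.952). Two losses do: 8/18 is S (0.916). The 30% and 40% examples above stay S throughout.

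**The case against.** The strongest objection concerns *either*. In a positive requirement it ordinarily means that one is enough. The Day 1 infusion then keeps a held DLT patient in the set, and the loss disappears. This stands: the loss of DLT patients depends on the reading. But the one-drug reading leaves the 80% test with almost nothing to do and moves the mismatch to patients without a DLT.

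Secondly, doses withheld under the protocol might not be part of the required dose, since the excuse for reductions aims at non-compliance. That is arguable, but the text names reductions only, and protocol 7.7 and 9.6.1.2.4 record interruptions and reductions separately.

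Thirdly, the consequences are contained. Part A is descriptive, mTPI output is guidance (protocol 5.1), and the sponsor decides the RP2D with the investigators. Reasons for exclusion are tabulated, AEs leading to DLTs are listed, set assignment is reviewed and documented (SAP 5.1), and the SAP names no separate DLT-rate table. This limits the harm and would make a dropped patient visible. It does not correct the rate, and the review is given no rule for held DLT patients.

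Finally, not every hold is affected. A hold just over 3 days leaves 81% to 83%. A patient may also stop within Cycle 1 at the investigator's discretion, with non-resolution established later, and so still enter by the discontinuation route.

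**Conclusion.** The mismatch holds with high confidence: on neither reading of *either* does the set mirror the replacement rule. A downward effect on the DLT rate is possible but conditional. Through lost DLT patients, it needs 80% to be required of each drug, withheld doses to count as required, and at least one DLT patient with 33 or fewer of 42 doses who was not discontinued in Cycle 1. Through dilution, it needs the one-drug reading and under-dosed patients without a DLT. The documents give neither number, so the size is not fixed; the rates above are illustrations.

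A reader might infer three stronger things that the documents do not support:
- *Any DLT patient discontinued after Day 21 is lost.* Only one who is also below 80% is lost.
- *Dose decisions were distorted.* Live looks use patients evaluable for DLTs, whose number the replacement rule is meant to secure. The nine changed cells matter only if the MTD set fed those looks, and all lie below n = 20.
- *The reported rate is biased.* No affected patient is documented.

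The rationale for protocol amendment 3 cites a July 2021 data cut and remaining patients on treatment for at least 2 years, so dose selection appears to be over. The main exposure is the DLT rate reported on this set. It should be fixed.

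**What to change.** Replace the definition in protocol 10.2 and SAP 5.1 with:

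*Every dose-selection patient with a DLT in Cycle 1, whatever dose was taken and whenever treatment stopped; plus every dose-selection patient without a DLT who completed Cycle 1 with at least 80% of the required rogaratinib dose and at least 80% of the required atezolizumab dose. Reductions made under the protocol do not count as non-compliance.*

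Use this one meaning of evaluable in protocol 6.4.2 and 10.2 and in the SAP, including the counts read against Tables 10-1 and 6-1. Re-derive the set from existing data and report the DLT rate and the number evaluable. State that the definition was clarified after data were available.

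The cost is one definition in each document, wording to align the cross-references, and a small re-run of outputs, although protocol 5.2.3 plans no further analysis after primary completion. No new data and no replacement patients are needed, and no treatment rule changes. If the set was built on the one-drug reading, some under-exposed patients without a DLT will leave it, and the number evaluable may differ from 20.

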10.3 Variables and planned statistical analyses

10.3.1 Disposition of patients

The number of patients enrolled and included in each analysis set will be tabulated by region, country and center. A summary table will also be presented for the number of patients enrolled and the number and percentage of patients in each of the defined analysis sets. The reasons for patients excluded from each of the analysis sets will also be tabulated. In addition, the number of patients who were enrolled, treated and discontinued will be summarized. Reasons for discontinuation of study treatment will be tabulated.

10.3.2 Demographic and other baseline characteristics

Summary statistics (arithmetic mean, standard deviation, median, minimum and maximum for quantitative variables) will be presented. Frequency tables for qualitative data will be provided. Medical history findings will be summarized using MedDRA (Medical Dictionary for Regulatory Activities) terms (v.20.0 or later).

10.3.3 Efficacy variables

All efficacy variables evaluated using the RECIST v1.1 (see Appendix 16.2) are linked to the secondary objective of the study Part A (see Section 4). All variables evaluated using the iRECIST v1.1 (see Appendix 16.2) are exploratory only.

Efficacy data will be summarized using descriptive statistics and will be graphically displayed if appropriate. The correlation between pharmacodynamic parameters and selected safety, efficacy, or PK parameters may be graphically displayed. Further statistical analyses may be conducted.

23 MAY 2023 Version 6.0 Page: 137 of 181

10.3.3.1 Secondary efficacy variable

The secondary efficacy variable is objective response rate.

Objective response rate (ORR) is defined as the percentage of patients whose best response is either a complete response (CR) or partial response (PR). Patients for whom best tumor response is not CR or PR, as well as patients without any efficacy assessment will be considered non-responders. According to RECIST v1.1, confirmation of PR and CR is not required considering the nature of the study and the protocol requirements.

10.3.3.2 Exploratory efficacy variables

Exploratory efficacy variables will include disease control rate (DCR) and duration of response (DOR), progression-free survival (PFS) and overall survival (OS).

These variables are defined according to RECIST v1.1 as below:

Disease control rate (DCR) is defined as the percentage of patients, whose overall best response was not progressive disease (i.e. CR, PR, SD or Non CR/Non PD). Tumor assessments with SD as response, that is performed prematurely after assignment to treatment of the patient (i.e. substantially earlier than the first planned radiological tumor assessment at 9 weeks), will not be taken into account.

Duration of response (DOR) (for PR and CR) is defined as the time from the first documented objective response of PR or CR, whichever is noted earlier, to disease progression or death (if death occurs before progression is documented). DOR will be defined for responders only, i.e. patients with a CR or PR. The actual dates the tumor scans were performed will be used for this calculation. DOR for patients who have not progressed or died at the time of analysis will be censored at the date of their last tumor assessment.

Progression-free survival (PFS) is defined as the time (days) from start of study treatment to date of first observed disease progression (investigator's radiological or clinical assessment) or death due to any cause, if death occurs before progression is documented. The actual date that the tumor scan was performed will be used for this calculation. If a tumor assessment is performed over more than one day (e.g. scans for chest and abdomen done on different days for the same evaluation), the earliest date will be used for the calculation of PFS. For patients without documented radiological or clinical progression or death at the time of analysis, PFS will be censored at the last actual visit date of tumor evaluation.

Overall survival (OS) is defined as the time from start of study treatment to death due to any cause. Patients alive at the date of data cut-off for analysis will be censored at the last date known to be alive. If a patient is lost to follow-up before any assessment after assignment to treatment, this patient will be censored at 1 day.

